2 STUDY OBJECTIVES

2.1 Study Overview

The overall goal of this Phase Ib/2 study is to identify a safe dose of chitosan for pharmacologic reduction of AGE levels in PCa subjects.

2.2 Primary Objective

The primary objective is to determine the maximum tolerated dose (MTD) of chitosan in subjects with PCa on ADT. The MTD will be defined as the dose that produces no more than 1 dose-limiting toxicity (DLT) in 6 subjects.

2.3 Secondary Objectives

The mechanistic studies under this section are to document any systemic effects from the chitosan treatment, related magnitude and timing of AGE depletion to chitosan effects, and determine if chitosan can reduce tissue, as well as serum, AGE levels.

- Identify systemic effects of chitosan on redox status (RedoxSys, serum oxidized glutathione), inflammation (plasma cytokines, Toll-like receptor signaling), and insulin resistance (HOMA-IR).
- Determine if chitosan modifies bowel permeability (plasma endotoxin) and microbiome diversity (16s rDNA sequencing).
- Correlate changes in serum AGE levels (pan-AGE, carboxymethyllysine, methylglyoxal, pentosidine adducts) with changes in tissue AGE levels as determined by skin autofluorescence.
- Define the frequency of a $\geq 30\%$ reduction in total AGE levels from the pretreatment level. A frequency of 50% will be considered “interesting” for further study.

3 SUBJECT SELECTION

3.1 Inclusion Criteria

1. Confirmation of adenocarcinoma of the prostate that is documented by one of the following: pathology report or clinic note with documented history of prostate cancer.
2. Subjects must be receiving ADT with a GnRH agonist or antagonist, with or without an anti-androgen or testosterone synthesis inhibitor. The current testosterone level must be documented to be $<50\text{ng/dL}$ at enrollment. Subjects whose ADT is interrupted may enroll or continue on study as long as the testosterone is documented to remain $<50\text{ng/dL}$ for the entire duration of study participation. Subjects who have undergone orchiectomy are also eligible.
3. Subjects must have adequate hematologic, renal, and hepatic function at baseline, as follows:
 - Hematology parameters: ANC $>1000/\text{mcL}$, platelets $>100,000/\text{mcL}$, Hgb $>8.0\text{gm/dL}$

- Renal Function: eGFR of ≥ 45 mls/min using Cockcroft and Gault formula
 - Liver Function: Total bilirubin \leq ULN, AST and ALT <1.5 x ULN
4. Able to swallow and retain oral medication
 5. ECOG performance status of 0 – 2
 6. Ability to sign written informed consent
 7. Testosterone level <50 ng/dL at time of enrollment.
 8. Age 18 or older.
 9. May have had prior radiation therapy, surgery, or cryoablation for primary prostate cancer
 10. May have had prior cytotoxic chemotherapy for metastatic prostate cancer, prior treatment with genomically-targeted agents, or Provenge

3.2 Exclusion Criteria

1. Known allergy to chitosan or shellfish.
2. History of receiving more than 2 classes of ADT.
3. Chronic constipation (BM < 3 x weekly), history of malabsorption or history of daily laxative use.
4. Patients requiring medication administration with lunch or dinner or at a frequency of three or more times per day are not eligible.
5. Current use of chitosan, sevelamer, and/or glucosamine.
6. Patients currently on diclofenac or any of the restricted therapies listed in section 4.5

3.3 Study Registration

The SIS Unit will provide patient registration services for this study. The SIS unit will conduct a patient eligibility audit review of all redacted eligibility source documents prior to patient registration. After obtaining signed informed consent and completion of required baseline assessments, eligible subjects will be registered. A unique subject number will be assigned to each patient. The SIS Unit will issue a patient registration confirmation email to the enrolling study team at the time of registration. This confirmation will include the patient's assigned cohort dose level and study ID number.

4 TREATMENT ADMINISTRATION

4.1 Androgen deprivation therapy

During the course of the study, subjects will continue to receive ADT therapy per subject's primary oncologist. Changes to ADT administration will be made at their discretion, but the testosterone level should remain <50 ng/dL during the entire study..

4.2 Chitosan administration

Subjects will be enrolled sequentially into four cohorts; the starting dose level is cohort 1. These cohorts will take chitosan as described in Table 2. Three patients will be enrolled into cohort 1, and no patients will be enrolled into the next cohort until the final patient in cohort 1 will have completed 28 days of treatment.

Chitosan will be taken up to 30 minutes before, or during, the middle and evening meals (BID dosing) or the largest meal of the day (Q day dosing). Chitosan will not be taken with breakfast, and the subjects should endeavor to take any chronic medicines before or with breakfast to minimize the chance of absorption of pharmaceuticals to chitosan. Any pharmaceuticals should be taken at least 1 hour before or 2 hours after chitosan. Any chitosan doses lost through vomiting will not be made up.

Cohort	Chitosan
-1	500mg Q day
1	500mg BID
2	1000mg BID
3	1500mg BID
4	2000mg BID

4.3 Medication Compliance Assessment

Patients will be required to track daily doses of study drugs by maintaining a daily medication diary. The subject will be asked to bring his drug diary and pill bottle back for each clinic visit to assess drug compliance.

4.4 Discontinuation of Therapy

Participation in this study should be discontinued for any of the following reasons:

- Change in anti-cancer therapy
- Procedures requiring general anesthesia.
- Development of any medical condition that, in the opinion of the treating physician, requires discontinuation of the study intervention
- Withdrawal of consent by the subject
- Evidence of allergic reaction to any component of the treatment regimen
- Any grade 3-4 hematologic or non-hematologic toxicity (other than in 4.5) that does not resolve, with drug discontinuation, to grade 1 or less in 14 days.

4.5 Restricted Therapies During Study Therapy

Current use of chitosan, sevelamer, and/or glucosamine.

Drugs Eliminated by Biliary Excretion (defined as greater than 4% excretion in bile):

- Chemotherapeutic Agents
 - Irinotecan
 - Paclitaxel
 - Vincristine
- Anti-Hyperlipidemics
 - Ezetimibe
 - Fluvastatin
 - Pravastatin
 - Rosuvastatin
 - Simvastatin
- Anti-Hypertensives
 - Ramipril
 - Spironolactone
 - Valsartan
- Analgesics
 - Acetaminophen
- NSAIDS
 - Diclofenac
 - Indomethacin
- Anti-histamines
 - Desloratadine
 - Fexofenadine
 - Levocetirizine
- Anti-diabetics
 - Rosiglitazone
- Immunosuppressants
 - Mycophenolic acid
- Anti-Psychotics
 - Quetiapine
- Anti-retrovirals
 - Lopinavir
 - Ritonavir
- Antibiotics
 - Ceftriaxone
 - Trovafloxacin
- Others
 - Cyclobenzaprine
 - Ketoconazole
 - Montelukast

4.6 Supportive Care during Therapy

It is unlikely that specific supportive care interventions will be needed for the study interventions. General supportive care for the subjects will be at the discretion of the treating physician.

5 SCHEDULE OF INTERVENTIONS AND ASSESSMENTS

5.1 General Considerations

- Informed consent must be signed prior to any study-specific assessments being done
- Screening assessments may be done up to 28 days prior to registration. Screening assessments completed within 28 days of day 1 do not have to be repeated.
- Day 85 or End of Study Assessments may be done +/- 3 days.
- All research and clinical blood samples must be collected while the subject is fasting.

5.2 Assessments and Procedures

The following clinical assessments are made at the time subjects are screened for the trial. Some of these may need to be repeated prior to day 1; see Appendix A for more details regarding the schedule of procedures and assessments.

- A full medical history and physical examination to review patient medical history, medication list, overall health and any side effects they may be experiencing. Medical history will include:
 - Extent of cancer to include metastatic disease
 - Concomitant medications
 - current ADT therapy
- Height, weight
- CBCD
- CMP (sodium, potassium, chloride, bicarbonate, BUN, creatinine, glucose, albumin, alkaline phosphatase, AST, ALT, calcium)
- PSA, testosterone
- Research blood, urine, and stool samples as outlined (see Appendix A)
- 24hr food intake recall questionnaire
- Quality of life questionnaires (FACT-P and AUA; see Appendices B, C)
- Measurement of tissue AGE level by skin autofluorescence using the AGE Reader device.

On day 29 of the study, a phone call will be made to the patient to assess any possible adverse events (AEs).

The following clinical assessments are made on day 85/End of study

- Interim medical history and focused physical exam to review:
 - Changes to the patient's medical history,
 - Changes to ADT

- Changes to familial history of diabetes
- Change to medication list
- Overall health and any side effects they may be experiencing.
- Height, weight
- CBCD
- CMP (sodium, potassium, chloride, bicarbonate, BUN, creatinine, glucose, albumin, alkaline phosphatase, AST, ALT, calcium)
- PSA
- Research blood and urine samples as outlined (see Appendix A)
- 24hr food intake recall questionnaire
- Measurement of tissue AGE level by skin autofluorescence using the AGE Reader device.
- Day 85: Quality of life questionnaires (FACT-P and AUA; see Appendices B, C)

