8 ADVERSE EVENTS

8.1 Definitions

Adverse Events (AE). An AE is defined as any untoward medical occurrence in a patient or clinical investigation subject administered a pharmaceutical product and that does not necessarily have to have a causal relationship with this treatment. An AE can therefore be any unfavorable and unintended sign (including an abnormal laboratory finding), symptom, or disease temporally associated with the use of the study drugs, whether or not is it causally related. During clinical trials, adverse events can be spontaneously reported or elicited during open-ended questioning, examination, or evaluation of a subject. (In order to prevent reporting bias, subjects should not be questioned regarding the specific occurrence of one or more adverse events.)

Adverse events will be named and graded using CTCAE v 5.0 and will be recorded prospectively during the study and entered into the REDCap database. Adverse events will be reported from the first day of study intervention until the last day of study intervention.

Serious Adverse Event (SAE). An SAE is any untoward medical occurrence that at any dose:

- results in death,
- is life-threatening (defined as an event in which the patient was at risk of death at the time of the event; it does not refer to an event which hypothetically might have caused death if it were more severe),
- requires inpatient hospitalization or causes prolongation of existing hospitalization,
- results in persistent or significant disability/incapacity,
- is a congenital anomaly/birth defect,
- results in the development of drug dependency or drug abuse,
- is an important medical event (defined as a medical event(s) that may not be immediately life-threatening or result in death or hospitalization but, based upon appropriate medical and scientific judgment, may jeopardize the patient or may require intervention (e.g., medical, surgical) to prevent one of the other serious outcomes listed in the definition above.) Examples of such events include, but are not limited to, intensive treatment in an emergency room or at home for allergic bronchospasm; blood dyscrasias or convulsions that do not result in hospitalization.

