AEs should be followed to resolution or stabilization, and reported as SAEs if they become serious. This also applies to subjects experiencing AEs that cause interruption or discontinuation of study

drugs, or those experiencing AEs that are present at the end of their participation in the study; such subjects should receive post-treatment follow-up as appropriate. All SAEs must be collected which occur within 30 days of discontinuation of dosing or completion of the patient's participation in the study if the last scheduled visit occurs at a later time.

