APPENDIX A. SCHEDULE OF PROCEDURES AND ASSESSMENTS

Study Activity	Screen ^c	Day 1 ^c	Day 14 ^g	Day 29	Day 57 ^g	Day 85/ End of study ^{a, d}	Specimen	
Demographics	X							
Full Physical Exam,	X							
Focused Physical Exam,		X				X		
Medical History to include: 
 • Duration of ADT • Extent of cancer • Personal history of diabetes mellitus • Current medications 	X	X						
Interim Medical History		X				X		
Anthropometric Measurements (height, weight)	X	X				X		
CBCD	X	X				X		
CMP (fasting) ^g	X	X				X		
Phosphorus	X	X				X		
PSA	X	X				X		
Assessment of toxicity		X	X ^g	X ^g	X ^g	X		
testosterone	X	X				X		
Chitosan			X-----X					
Drug diary review ^e						X		
Informed consent	X							
Insulin Resistance (HOMA-IR)		X ^f				X	Plasma ^b	
CRP, AGE species and precursors		X ^f				X	Serum ^b	
RedOx status (ORP, reduced glutathione)		X ^f				X	Plasma ^b	
RAGE, TLR expression, signaling		X ^f				X	Whole blood ^b	
Microbiome profiling		X ^f				X	Stool	
AGE species		X ^f				X	Urine ⁱ	
Tissue AGE level by autofluorescence		X				X		
Food Recall Dietary AGE content ^h		X ^f				X		
QOL (FACT-P and AUA)		X ^f				X		

- All days are +/- 5 days
- 2x7mL EDTA blood (=plasma), 2x7mL clot tube (=serum), 1x7mL sodium heparin tube (=whole blood).
- Screening assessments to be done within 28 days of registration. Screening assessments may be used for the day 1 assessments if they were completed within 28 days of day 1. The CMP used for eligibility confirmation does not have to be fasting, but a fasting CMP will need to be collected prior to day 1 drug administration. Fasting is defined as nothing containing calories since the previous midnight.
- If the subject goes off study less than 2 weeks after start of dosing, "end of study" labs and questionnaires will not be done.
- The drug diary will be given to each subject for completion during the study.
- Research procedures (excluding informed consent) may be done at any point after informed consent and prior to first dose of drug (on day 1). Research blood, urine and stool samples will be taken to the participating research lab(s) for processing.

NCT # NCT03712371

CTO # 102928

Version Date: 09/09/2020

- g) On day 14, day 29, and day 57 (+/- 5 days), compliance and adverse events will be assessed via phone using the phone contact guide in appendix D.
- h) Food recall using the NCI quick food scan and the NIH's "Eating at America's Table Study" Quick food scan.

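### Section 8.2 collects SAEs for 30 days after dosing, but no contact is scheduled after the day 85 or end-of-study visit, and section 7.4 ends data collection on withdrawal

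*Combined protocol and SAP*

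**What the plan says.** **After dosing.** Section 8.2 sets the collection rule: "All SAEs must be collected which occur within 30 days of discontinuation of dosing or completion of the patient's participation in the study". The second trigger applies when the last scheduled visit is later than the last dose. Patients whose AEs interrupted or stopped the drug, or are present at the end, get a looser provision: "such subjects should receive post-treatment follow-up as appropriate". No time or method is attached to it. Section 8.1 limits ordinary AE reporting: "Adverse events will be reported from the first day of study intervention until the last day of study intervention".

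Section 5.2 ends its schedule with the list introduced by "The following clinical assessments are made on day 85/End of study". In Appendix A the row "Assessment of toxicity" is marked at days 1, 14, 29, 57 and 85/end of study, and no column follows.

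Section 7.4 says that if a subject withdraws or is withdrawn, the team stops gathering new information and specimens. What is already in hand may still be analysed.

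**During dosing.** Section 5.2 mentions one call: "On day 29 of the study, a phone call will be made to the patient to assess any possible adverse events (AEs". Appendix A, footnote g, has three: "On day 14, day 29, and day 57 (+/- 5 days), compliance and adverse events will be assessed via phone". Section 5.7, on the schedule of assessments, only refers the reader to Appendix A. Section 5.2 also points there, in its screening paragraph.

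**The concern.** A rule that all SAEs in a period be collected needs a step that asks about them. Here the period begins at about the time the last scheduled contact takes place. A patient who finishes treatment well and is admitted to hospital three weeks later falls inside the 8.2 window, but nobody is scheduled to ask.

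Patients who leave early are worse placed, because 7.4 can be read as forbidding the enquiry that 8.2 requires. Section 4.4 is titled as discontinuation of therapy but speaks of ending participation in the study, including for unresolved grade 3-4 toxicity and for allergic reaction. Those are patients in whom a later SAE would be especially informative.

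At stake is the completeness of the SAE record. The expansion cohort is meant in part to define toxicity better (section 10.2), and 8.2 wants SAEs whether or not they are related to the drug.

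The on-treatment discrepancy is smaller. A reader of 5.2 alone would make one AE call where Appendix A expects three.

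**Working it through.** The plan gives no figure of its own on this point. The check compares the sections and counts days.

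**Inputs.** Contact days come from section 5.2 and Appendix A, the 30-day SAE window from 8.2, the end of AE reporting from 8.1, the withdrawal rule from 7.4, and maximum accrual (54) from 10.2.

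**1. End of the SAE window.** Window end = day of last dose + 30.
- Last dose on day 85: 85 + 30 = day 115.
- With the ±5 days that Appendix A allows, and assuming the last dose coincides with that visit: 80 + 30 = day 110 to 90 + 30 = day 120.
- If the last scheduled visit falls after the last dose, 8.2 counts the 30 days from completion of participation instead.

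**2. Scheduled contacts inside the window.** Both 5.2 and Appendix A stop at the day 85 or end-of-study visit. The count after that visit is 0 under either, for each case in step 1.

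**3. Who is left without planned follow-up.** The provision in 8.2 for follow-up as appropriate covers patients with an AE that interrupted or stopped the drug, or that is present at the end. Everyone else has none. Since 8.1 closes AE reporting with the intervention, the gap concerns SAEs only.

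**4. Early leavers.** Under 8.2 a patient who stops on day *d* is owed SAE collection to about day *d* + 30. Under 7.4, if that patient withdraws or is withdrawn, collection of new information stops. Both cannot be followed for the same patient.

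**5. Intervals between AE enquiries on treatment, counted from day 1.**

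| Source | Contacts after day 1 | Intervals (days) | Longest |
|---|---|---|---|
| Section 5.2 | 29, 85 | 29 − 1 = 28; 85 − 29 = 56 | 56 |
| Appendix A | 14, 29, 57, 85 | 14 − 1 = 13; 29 − 14 = 15; 57 − 29 = 28; 85 − 57 = 28 | 28 |

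The two sources share the day 29 call and the day 85 visit. They differ in the day 14 and day 57 calls.

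**6. Cost of a post-dose call.** One call × at most 54 patients = at most 54 calls.

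**The case against.** **A collection duty does not require a scheduled call.** Subjects stay on ADT under their oncologist (section 4.1), and section 7.2 says the investigators will already be treating them. An admission may well reach the site through routine care, and 8.2 has AEs followed to resolution or stabilization. This stands as far as it goes. A reader might infer that the 30-day rule cannot be met, or that SAEs surface only when the patient volunteers them. The documents support neither reading. What remains is that no planned step asks patients who have no qualifying AE.

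**Appendix A governs the schedule.** Section 5.7 defers to it, 5.2 points to it, and 5.2 does not say that day 29 is the only call. This largely stands: 5.2 is an incomplete summary, not a rival schedule. A reader might infer that two centres will collect AEs on different schedules. That is conjecture, as the second centre is still to be determined (section 5.3). The deferral does not help after day 85, where the two sources agree and both are silent.

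**The primary objective is little affected.** A reader might infer that DLT ascertainment turns on which section a site follows. Both have the day 29 call, nominally just after the 28-day DLT window. The ±5 days in Appendix A would allow it on day 24 (29 − 5), but that comes from the tolerance, not from the number of calls. The hypophosphatemia DLT is a laboratory finding that no phone call would detect. The day 14 call would help date the onset and resolution of symptomatic DLTs, but the documents do not show that DLTs would be missed without it.

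**A call to every early stopper would collide with 7.4.** This stands, and it shapes the fix: 7.4 must be reconciled with 8.2, and patients who withdraw consent to follow-up must be left out.

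**Conclusion.** The point holds as a gap between the SAE rule and the schedule. In the 30 days after dosing there are 0 scheduled contacts whichever section is followed, and 7.4 conflicts with 8.2 for subjects who withdraw or are withdrawn. It is worth correcting because the remedy is specific and cheap.

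The missing day 14 and day 57 calls in 5.2 are a separate, minor consistency matter: a longest interval of 56 days against 28 for a site that reads 5.2 alone.

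The day 115 figure assumes that dosing ends on day 85. The documents give no SAE rate for this population, so the number of events that might be missed cannot be estimated, and nothing shows that any data have been lost. The phone contact guide cited as Appendix D is not in the text available, and nothing is inferred from that.

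**What to change.** 1. Add to Appendix A and section 5.2 one phone contact about 30 days after the last dose, limited to SAEs, for every treated patient who has not withdrawn consent to follow-up. Where participation ends after the last dose, time it to the later trigger in 8.2.
2. Reconcile 7.4 with 8.2. Separate withdrawal of consent to follow-up from being taken off treatment, and state that patients in the second group stay within the 30-day SAE window.
3. As a minor edit, change 5.2 to name the day 14, 29 and 57 calls for compliance and AEs, with a reference to footnote g of Appendix A.

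The cost is the wording of an amendment and at most 54 short calls by existing staff. No analysis or sample size changes.

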5.3 Subject Recruitment

This study will take place at the MUSC and one other cancer center (to be determined).

- Subjects will be identified by the designated IRB approved study team or will be referred by colleagues who care for the patient populations under study.
- Designated IRB approved study research team personnel may screen records to identify potential subjects. Records and/or areas that may be reviewed include pathology/surgical reports, and pharmacy records.
- Potential subjects will only be approached for the study after they have been informed of the study by someone involved with their clinical care.
- Potential subjects who have previously agreed to be contacted for research may be approached by the study team.

5.4 Informed Consent Process

- Subjects who are interested in participating will be interviewed in clinic. A designated IRB approved member of the study will explain the nature of the study, the benefits and risks. Informed consent will be obtained by designated IRB approved research members in clinic. Consent will be documented by obtaining the subject's signature on the approved consent form, and documenting the consent process through a progress note in the participant's clinical or research record.
- Consent may be obtained the same day the patient is presented with the trial.

